9.7.4 Planned Analysis for the Secondary Objectives

9.7.4.1 To describe the characteristics of AF patients exposed and unexposed to OAC

The sociodemographic characteristics, comorbidities, medical history of interest and concomitant treatments will be described at index date in terms of:

- Mean, SD, median, Q1, Q3, min and max for every continuous variable.
- Counts and percentages of patients per category for every binary and categorical variable.

The analysis will be performed in AF incident patients, overall and according to the exposition status at index date (exposed or unexposed to OAC). Patient characteristics will be displayed by calendar year from 2016 to 2019 and over the 4-year period 2016-2019.

In addition, patient characteristics will be also described, overall and according to the exposition status at index date (exposed or unexposed to OAC), **for the population of AF incident patients excluding those with a reported outcomes of interest up to 30 days prior index date** (i.e. population studied in incidence rates for

each event of interest (stroke, major bleeding and death) and in Cox model analysis) for the 4-year period 2016-2019.

9.7.4.2 Comparison of the incidence of stroke, major bleeding, death

Analyses will be performed independently for each event of interest stroke, major bleeding and death.

Survival analysis will be performed to compare incidence rate (stroke, major bleeding or death) in AF incident patients exposed and unexposed to OAC therapy **excluding those with a reported outcomes of interest up to 30 days prior index date**, using a Cox regression model. The Cox regressions models will consider the first event of interest occurring in AF incident patients exposed and unexposed to OAC. OAC exposure will be considered as time-dependent variable and the models will be adjusted for covariates defined below. By applying the OAC exposure variable as a time dependent variable, estimates of Hazard Ratio will account for switches and discontinuations. Time-dependent exposure Cox proportional hazards models will be used to estimate:

- The Crude hazard ratio (i.e. the incidence rate ratio), and therefore the risk of each outcome at any point during the follow-up since index date
- The adjusted hazard ratio on potential confounders including patient:
 - Time-fixed confounders: sex, age (<80, 80-90, >90 years old), prescriber's specialty at initiation of OAC, having malnutrition (yes/no), risk of falls (yes/no), morbid obesity (yes/no), history of stroke (yes/no), history of major bleeding (yes/no), at least one visit to a nursing home (yes/no), history of dementia (yes/no), concomitant treatments (e.g. receiving at least one antiplatelet drugs (yes/no), other anticoagulant drugs (yes/no), etc. - cf. *Table XV for all confounders*)
 - Time-dependent confounders: AOC treatment exposure

In a first model, patient exposure will be modelled according to five categories: exposure to apixaban, dabigatran or rivaroxaban, exposure to VKA or unexposed patients. In a second model, exposure to DOACs will be integrated instead of exposure to apixaban, dabigatran or rivaroxaban. For both models, the reference for comparison will be VKA exposure.

Same models will be performed on AF incident patients with a high thromboembolic risk (if modified CHAD₂DS₂VASC score is ≥ 2 for males and ≥ 3 females). Patient exposure will be modelled according to three categories: exposure to DOAC (Apixaban, Dabigatran or Rivaroxaban), exposure to VKA or unexposed patients. The reference for comparison will also be VKA exposure.

Censor is defined as patient's last health record, or date of end of follow-up. Hazard ratios and associated 95% CI will be reported. Models will be considered valid if they meet the proportional hazards assumption as assessed by examination of Schoenfeld residuals and log-log plots. In case of the proportionality assumption is violated, the nonparametric additive hazard model (Aalen-model) with OAC exposure considered as time-dependent variable will be applied.

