3.5.3. Stratification

All analyses on AF patients will be stratified on age-group: <80, 80-90, > 90 years old.

All analyses on AF patients exposed and unexposed to OAC, will be stratified on modified CHA₂DS₂VASC score strata (18), low risk (score 0 in males or 1 in females); moderate risk (score 1 in males or 2 in females); high risk if ≥2 for males and ≥3 females.

All analyses where the event of interest is stroke, will be stratified on ischemic or hemorrhagic stroke.

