3.7.2.2 Comparison of the incidence of stroke, major bleeding, death

To compare the incidence of clinical outcomes, stroke, major bleeding and death, in AF patients exposed and unexposed to OAC therapy, in longitudinal analysis, we will use a comparison of cumulative incidence rate using a Cox regression model with OAC exposure considered as time-dependent variable adjusted for covariates (or IPTW if necessary) (Figure 2, Appendix 2). This analysis will be performed twice, firstly by comparing patients exposed to dabigatran, apixaban, rivaroxaban vs. patients exposed to VKAs and secondly for AF patients with a high thromboembolic risk (if modified CHA2DS2VASC score is ≥ 2 for males and ≥ 3 females) by comparing patients exposed to DOACs combined in one class vs. VKAs vs. unexposed patients for patients. By applying the OAC exposure variable as a time dependent variable, estimates of Hazard Ratio will account for switches and discontinuations. In this analysis, the reference will be VKA exposure. Censor is defined as patient's last health record or date of end of follow-up.

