9.2.3.5 Stratification groups

Stratification groups will be considered:

- Age groups (<80 , $80-90$, >90 years old);
- Modified CHAD₂DS₂VASC score strata (Low risk / Moderate risk/ High risk);
- Patients having a history of stroke (Ischemic / Hemorrhagic);
- Patients having a malnutrition (Yes / No);
- Patients at risk of falls identified by an algorithm adapted to SNDS data (Yes / No);
- Frail patients identified by Claims based Frailty Index (CFI) adapted to SNDS data (Yes / No);
- NVAF patients with one or more comorbidities identified by age adjusted Charlson comorbidity index (ACCI) adapted to SNDS data (Yes / No);
- Patients having a morbid obesity (Yes / No);
- Patients with a history of major bleeding;
- Patient with at least one visit to a nursing home;
- Patients with a history of dementia.

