End date of unexposed sequence	
Date variable
 
The end date of unexposed sequence is defined as:
 
 – The day before the Start date of treatment sequence if the patient starts an OAC 
OR
 
 – End of follow-up period in other cases

Second, each event of interest with the occurred dates available in the data extraction for the AF patients in France during their follow-up will be derived by treatment exposure sequence as indicated in [Table VIII](#).

Table VIII. Derived variables for identifying events of interest

Variable	Definition
Stroke (ischemic or hemorrhagic)	
Binary variable (Yes / No)
 
Equals to “Yes” if the patient is hospitalized with any discharge diagnosis (i.e., main, related or associated diagnosis) of stroke (ischemic or haemorrhagic)

	
ICD-10 codes: I60.x, I61.x, I62.9, I63.x, I64.x, G45.x, G46.x, G81.x, S06.4, S06.5, S06.6
 
Equals to “No” in other cases

Major bleeding	
Binary variable (Yes / No)
 
Equals to “Yes” if the patient is hospitalized with any discharge diagnosis (i.e., main, related or associated diagnosis) of major bleeding
 
ICD-10 codes: I60.x, I61.x, I62.9, S06.4, S06.5, S06.6, I85.0, K22.6, K25.0, K25.2, K25.4, K25.6, K26.0, K26.2, K26.4, K26.6, K27.0, K27.2, K27.4, K27.6, K28.0, K28.2, K28.4, K28.6, K29.0, K62.5, K92.0, K92.1, K92.2, D62, H35.6, H43.1 H45.0, H92.2, I31.2, J94.2, R04.x, K66.1, M25.0, N02, N93.8, N93.9, N95.0, R31, R58, T79.2
 
Equals to “No” in other cases

Death	
Binary variable (Yes / No)
 
Equals to “Yes” if the date of death is reported in DCIR
 
Equals to “No” in other cases

Date of occurrence	
Date variable
 
Equals to the value of date when occurred the event

In the case of a patient presents an event of interest during the grace period, which ends after the end of the study, the event will be considered neither in an exposed nor in an unexposed period, and the patient will be censured at the end of the study period.

Then, the variable presented in [Table IX](#)[Table X](#) will be derived for the analyses of incidence, for each patient, for each event of interest and for each exposure treatment sequence.

Table IX. Derived variables for the analyses of incidence rate on events of interest

Variable	Definition

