3.3. Comparison of the incidence of stroke, major bleeding, death

Table A10. Risk of stroke, major bleeding or death in AF incident patients

	Event		Crude risk ¹		Adjusted risk ^{2,*}	
	n	%	HR	[95%CI]	HR	[95%CI]
Risk of stroke						
Exposure to DOACs	xx	(x.x)	x.xx	[x.xx-x.xx]	x.xx	[x.xx-x.xx]
Exposure to Apixaban	xx	(x.x)	x.xx	[x.xx-x.xx]	x.xx	[x.xx-x.xx]
Exposure to Dabigatran	xx	(x.x)	x.xx	[x.xx-x.xx]	x.xx	[x.xx-x.xx]
Exposure to Rivaroxaban	xx	(x.x)	x.xx	[x.xx-x.xx]	x.xx	[x.xx-x.xx]
Unexposed to OAC**	xx	(x.x)	x.xx	[x.xx-x.xx]	x.xx	[x.xx-x.xx]
Exposure to VKA	xx	(x.x)	ref		ref	
Risk of major bleeding						
Exposure to DOACs	xx	(x.x)	x.xx	[x.xx-x.xx]	x.xx	[x.xx-x.xx]
Exposure to Apixaban	xx	(x.x)	x.xx	[x.xx-x.xx]	x.xx	[x.xx-x.xx]
Exposure to Dabigatran	xx	(x.x)	x.xx	[x.xx-x.xx]	x.xx	[x.xx-x.xx]
Exposure to Rivaroxaban	xx	(x.x)	x.xx	[x.xx-x.xx]	x.xx	[x.xx-x.xx]
Unexposed to OAC**	xx	(x.x)	x.xx	[x.xx-x.xx]	x.xx	[x.xx-x.xx]
Exposure to VKA	xx	(x.x)	ref		ref	
Risk of death						
Exposure to DOACs	xx	(x.x)	x.xx	[x.xx-x.xx]	x.xx	[x.xx-x.xx]
Exposure to Apixaban	xx	(x.x)	x.xx	[x.xx-x.xx]	x.xx	[x.xx-x.xx]
Exposure to Dabigatran	xx	(x.x)	x.xx	[x.xx-x.xx]	x.xx	[x.xx-x.xx]
Exposure to Rivaroxaban	xx	(x.x)	x.xx	[x.xx-x.xx]	x.xx	[x.xx-x.xx]
Unexposed to OAC**	xx	(x.x)	x.xx	[x.xx-x.xx]	x.xx	[x.xx-x.xx]
Exposure to VKA	xx	(x.x)	ref		ref	

AF : Non Valvular Atrial Fibrillation; HR: hazard ratio; 95%CI: 95% confidence interval

Note: For considering DOAC treatment in models, two regressions models will be performed for this table: one model with "Exposure to DOACs" as independent variable; second model with exposure for each molecule within the class of DOAC (Apixaban, Dabigatran, Rivaroxaban).¹From a time-dependant exposure to OAC Cox proportional hazards model

²From a time-dependant exposure to OAC and time-fixed covariates Cox proportional hazards model;

*Adjusted on the following covariates at index date: age (<80, 80-90, >90 years old), sex, having malnutrition, risk of falls, morbid obesity, history of stroke, history of major bleeding, at least one visit to a nursing home, history of dementia, each concomitant treatments

**Unexposed to OAC correspond to the period where the patients are not exposed to OAC.

Same table will be presented for sensitivity analyses:

- with integration of 2020 data

- with 30 days and 90 days of maximal number of days allowed for being refilled

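### The Cox comparison models stroke only as one pooled outcome, although Protocol 3.5.3 requires every analysis of stroke to be split into ischemic and hemorrhagic type

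*SAP*

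**What the plan says.** Protocol 3.5.3 sets a general rule: "All analyses where the event of interest is stroke, will be stratified on ischemic or hemorrhagic stroke". Protocol 3.7.2.2 puts stroke among the Cox outcomes: "To compare the incidence of clinical outcomes, stroke, major bleeding and death, in AF patients exposed and unexposed to OAC therapy". The rule therefore covers the Cox analysis.

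The SAP treats stroke as follows.

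- **Event definition.** Table VIII (9.4.2) derives one yes/no stroke event from the list "I60.x, I61.x, I62.9, I63.x, I64.x, G45.x, G46.x, G81.x, S06.4, S06.5, S06.6", the same list that Table V uses for previous stroke. It combines ischemic, unspecified, transient ischemic and hemorrhagic codes.
- **Models.** Section 9.7.4.2 says "Analyses will be performed independently for each event of interest stroke, major bleeding and death" and "The Cox regressions models will consider the first event of interest occurring in AF incident patients exposed and unexposed to OAC". On the exposure contrast it adds "For both models, the reference for comparison will be VKA exposure".
- **Shells.** "Table A10. Risk of stroke, major bleeding or death in AF incident patients" has one stroke block. So does Table A11, its counterpart for high thromboembolic risk. Neither set of footnotes adds a split.
- **Sensitivity analyses.** Section 9.7.6 adds no split.
- **Where the split appears.** Table A3 gives ischemic and hemorrhagic incidence rates separately. Table XXI mentions type of stroke once, in its stratification row.

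Section 5 of the SAP records no amendments, and nothing explains why the Cox models leave the split out.

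**The concern.** Objective 3 is the study's only multivariable comparison of stroke between exposure groups. Protocol 2.1 says that treatment aims above all to prevent ischemic stroke and that the main risk of OAC is serious bleeding. A pooled stroke outcome mixes an event that OAC is meant to prevent with one that it may cause.

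The consequence depends on the contrast. For unexposed versus VKA, the two types may move in opposite directions, and the pooled HR would then partly offset them. For DOAC versus VKA, both groups are anticoagulated. There the pooled HR blends two effects that need not be opposed, and a lower value could reflect fewer intracranial bleeds with no ischemic difference.

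The major bleeding HR does not resolve this. Table VIII also places I60, I61, I62.9 and S06.4 to S06.6 in the major bleeding list, alongside gastrointestinal, ocular, urinary and other codes. Intracranial bleeds enter both HRs and can be seen separately in neither.

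**Working it through.** **Step 1: the documents side by side.**

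| Place | Stroke split by type of event? |
|---|---|
| Protocol 3.5.3 | Required for all stroke analyses |
| SAP Table VIII (event variable) | No, one binary variable |
| SAP Table A3 (crude and age-standardized rates) | Yes |
| SAP 9.7.4.2 (Cox models) | No |
| SAP Tables A10 and A11 (Cox shells) | No |
| SAP 9.7.6 (sensitivity analyses) | No |

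The conflict needs no outside figure.

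**Step 2: how pooling works.** The plan states no event count, power or type-specific effect for the Cox analysis, so there is no figure of its own to reproduce. Let h be the hemorrhagic share of the stroke hazard in VKA time. For the first stroke of either type, the pooled hazard is the sum of the two type-specific hazards. With constant hazards,

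pooled HR = (1 − h) × HR_isch + h × HR_hem.

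The pooled HR therefore always lies between the two type-specific HRs.

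**Step 3: illustration. All inputs are assumptions.**

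Unexposed versus VKA, HR_isch = 2.0 and HR_hem = 0.5:
- h = 15%: 0.85 × 2.0 + 0.15 × 0.5 = 1.775, or 1.78
- h = 30%: 0.70 × 2.0 + 0.30 × 0.5 = 1.55
- h = 40%: 0.60 × 2.0 + 0.40 × 0.5 = 1.40

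DOAC versus VKA, HR_isch = 1.0 and HR_hem = 0.5:
- h = 20%: 0.80 × 1.0 + 0.20 × 0.5 = 0.90
- h = 40%: 0.60 × 1.0 + 0.40 × 0.5 = 0.80

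**Step 4: range.** For unexposed versus VKA, with HR_isch from 1.25 to 2.5, HR_hem from 0.4 to 0.8 and h from 10% to 40%, the pooled HR runs from 0.91 to 2.33. It equals 1 when h = (HR_isch − 1) / (HR_isch − HR_hem). For HRs of 2.0 and 0.5 that is 1.0 / 1.5, or 67%. Over the grid it lies between 29% (HRs 1.25 and 0.4) and 88% (HRs 2.5 and 0.8).

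**Step 5: simulation check.** In a simulated cohort of 200,000 with true HRs of 1.5 and 0.4 and h = 30%, the formula gives 0.70 × 1.5 + 0.30 × 0.4 = 1.17. Person-time rate ratios (95% CI) were 1.48 (1.41 to 1.56) for ischemic, 0.40 (0.36 to 0.44) for hemorrhagic and 1.15 (1.10 to 1.19) for pooled stroke. The split recovers both effects; the pooled estimate shows neither.

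**The case against.** The strongest reply has four parts.

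**The pooled endpoint is the protocol's own.** The primary objective defines stroke as ischemic or hemorrhagic, and the comparison is secondary. This is a reason to keep pooled stroke. It does not set aside the rule in 3.5.3.

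**The types can already be told apart.** A reader might infer that the study offers no view of the two types. That is not so: Table A3 gives rates by type with 95% CIs for unexposed time, VKA, DOACs and each drug, and crude rate ratios can be formed from them. These rates are at most age-standardized, however, while 9.7.4.2 adjusts for many other factors. What is missing is the multivariable HR by type.

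**The direction of bias is not documented.** This stands. A pooled HR understates the ischemic contrast only if the hemorrhagic HR for unexposed patients is lower than the ischemic one. The SAP describes contraindications to OAC but does not list them among its exclusions, so residual confounding could move the hemorrhagic HR either way.

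**The overlap with major bleeding counts no event twice in one estimate.** This also stands: the outcomes are modelled separately and never summed. The overlap limits interpretation; it is not an arithmetic error.

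Two further inferences fail. First, the SAP has not replaced the outcome split with its stratum for history of ischemic or hemorrhagic stroke. That stratum carries over a separate requirement in Protocol 3.7.4. Second, the single entry in Table XXI does not settle which objectives it covers, because the cell layout is unclear in the available text. Tables A10 and A11 are the firmer evidence.

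**Conclusion.** The SAP's Cox analysis omits, without explanation, a stroke-type split that the protocol requires. No multivariable HR for ischemic or for hemorrhagic stroke would be produced. This conclusion rests on the documents alone.

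The size of the effect rests on assumed HRs and shares. In the main illustration an ischemic HR of 2.0 appears as 1.78 to 1.40. For DOAC versus VKA, a null ischemic effect could appear as 0.90 to 0.80.

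A reader might infer that opposite OAC effects cancel in the stroke HR. The documents do not support that. They give no type-specific effects or shares, the main illustration shows attenuation only, and cancellation to 1 would need particular combinations of HRs and h. Opposite directions are plausible for unexposed versus VKA, but need not arise for DOAC versus VKA.

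**What to change.** 1. **Table VIII.** Add ischemic and hemorrhagic event variables using the code sets in Protocol Appendix 3. Reconcile I63.6, which the SAP's stroke-type history variable (Table VI) excludes but the outcome list includes. State how a stay with codes from both sets is classified.
2. **Section 9.7.4.2 and Table XXI.** Add cause-specific Cox models for first ischemic and first hemorrhagic stroke, with the same exposure coding and covariates. State whether an earlier stroke of the other type during follow-up censors the patient or follow-up continues.
3. **Shells.** Add both blocks to Tables A10 and A11, and to the sensitivity versions of A10. The SAP plans no sensitivity version of A11.
4. **Pooled stroke.** Keep it, with a footnote that hemorrhagic strokes are also counted in major bleeding.

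If the sponsor prefers not to split, the SAP should record and justify the departure from Protocol 3.5.3. Either choice should be fixed before results are seen.

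**Cost.** The event derivation has to be written, since Table VIII does not contain it. The models repeat existing code: 2 stroke types × 2 exposure codings = 4 adjusted fits per table version, with their crude counterparts. Intervals for hemorrhagic stroke will be wider; how much cannot be stated, because the plan gives no event counts.

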9.3.1.2 Main data available

The data available in DCIR and PMSI databases that are of importance for this study are as follows:

- Administrative data used for sociodemographic, including:
 - o Date of birth (month and year);
 - o Date of death;
 - o Sex;
 - o City, department and region of residence;
 - o CMU-C;
 - o Aid for complementary health care (ACS) for elderly patients.
- Outpatient care data, including:
 - o Health professionals visited, medical specialty for physicians, dates of visits;
 - o Dates of dispensation, dates of reimbursement, type and number of services carried out by the health professional, reimbursed costs and costs paid by the patients for the associate cares;
 - o Drugs coded according to ATC and CIP classifications;
 - o Medical and technical acts coded according to CCAM;
 - o Biological acts coded according to NABM;
 - o Medical devices coded according to LPPR;
 - o Medical transportations;
 - o Sick leaves;
- Inpatient care data, including:
 - o Type of stay coded according to DRG;
 - o Localization, type and identifier of hospitals;
 - o Dates and reasons for admissions and discharges;
 - o Main, related and significant associated diagnoses of admissions coded according to ICD-10;
 - o Drugs dispensed at hospital and costly innovative drugs administered during admissions, both coded according to ATC and the common unit of dispensation (28nité commune de dispensation, UCD) classification;
 - o Medical and biological acts performed during admissions and coded according to CCAM and NABM, respectively;
 - o Other information such as stays in resuscitation units or intensive cares.
- Medical data, including:
 - o Presence of a LTD status, start and end dates of LTD coverage and nature of LTDs coded according to ICD-10.

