9.4.3 Derived Variables for the Secondary Objectives

9.4.3.1 To describe the characteristics of AF patients exposed and unexposed to OAC

The sociodemographic characteristics, comorbidities, medical history of interest and concomitant treatments (respectively [Table XII](#), [Table XIII](#) and [Table XIV](#)) will be derived at start follow-up date for AF incident patients exposed and unexposed to OAC ([Table XI](#)).

Table XI. Derived variables for exposition to OAC

Variable	Definition
Exposed to OAC at index date	
Binary variable (Exposed to OAC/Unexposed to OAC)
 
Equals to ‘Exposed to OAC’ if the patient has at least one delivery of AOC (VKA, Apixaban, Dabigatran or Rivaroxaban) at index date (defined in 9.2.1.4)
 
ATC codes: B01AA, B01AF02, B01AF01, B01AE07
 
Equals to ‘Unexposed to OAC’ if the patient has no reimbursement for AOC at index date (defined in 9.2.1.4)Table III

Treatment at index date	
Categorical variable (VKA/Apixaban/Dabigatran/Rivaroxaban/Unexposed)
 
Equals to “VKA” if the patient has one reimbursement of VKA at -index date
 
Equals to “Apixaban” if the patient has one reimbursement of Apixaban at index date
 
Equals to “Dabigatran” if the patient has one reimbursement of Dabigatran at index date
 
Equals to “Rivaroxaban” if the patient has one reimbursement of Rivaroxaban at index date
 
Equals to “Unexposed” if the patient has any reimbursement of OAC at index date

Table XII. Derived variables for the sociodemographic characteristics

Variable	Definition
Age	
Continuous variable (year)
 
See Table III

Sex	
Binary variable (Female / Male)
 
See Table III

Complimentary universal health care (CMU-c)	
Binary variable (Yes / No)
 
Equals to “Yes” if the patient benefits from an exemption from care on the grounds of CMU-c for care received on the index date
 
Equals to “No” in other cases

Aid for complementary health care (ACS) for elderly patients	
Binary variable (Yes / No)
 
Equals to “Yes” if the patient benefits from an aid for complementary health care on the index date
 
Equals to “No” in other cases

Region of residence	Categorical variable (Île de France, Centre-Val de Loire, Corse, etc.) Derived based on the code of the department of residence recorded with health cares carried out on index date
Frail patient	Binary variable (Yes / No) See Table VI

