9.4.3.2 Comparison of the incidence of stroke, major bleeding, death

The incidence rate ratio for each event of interest (stroke, major bleeding and death; see [Table VIII](#) for derivation of events of interest) will be compared using a Cox regression model with OAC exposure (see [Table VII](#) for derivation of exposure sequences) considered as time-dependent variable adjusted for covariates. Covariates will be derived at index date as indicated in [Table XV](#).

Table XV. Derived variables for confounders

Variable	Definition
Age	Categorical variable (<80 years old / 80–90 / >90 years old) See Table III
Sex	Binary variable (Female / Male) See Table III
Prescriber's specialty at initiation of OAC	Categorical variable (Hospital-based physician/ City cardiologist/ Generalist practitioners/Other) See Table III
Having Malnutrition	Binary variable (Yes / No) See Table III
Risk of falls	Binary variable (Yes / No) See Table III
Frail patients	Binary variable (Yes / No) See Table V
Morbid obesity	Binary variable (Yes / No) See Table VI
At least one visit to a nursing home	Binary variable (Yes / No) See Table VI
Concomitant treatments	Binary variable (Yes / No) for each concomitant treatment listed in Table XIV

For example, for antiplatelet drugs, equals to “Yes” if the patient has at least one reimbursement for an antiplatelet drug in the 4 months before the index date
	
HAS-BLED score	Categorical variable (0, 1, 2, 3, ≥ 4) See Table VI
CHAD₂DS₂VASC score	Categorical variable (0, 1, 2, 3, 4, ≥ 5) See Table VI
Age adjusted Charlson Cormordity Index (ACCI) adapted to SNDS data	Categorical variable (0, 1-2, 3-4, ≥ 5) See Table VI XII

9.4.3.3 *Estimation of the AF annual standardized incidence rate and prevalence*

All the variables in [Table XVI](#) will be derived for all AF patients in France in 2016, 2017, 2018 and 2019.

Table XVI. Derived variables for incidence and prevalence

Variable	Definition
Incident AF patient	Binary variable (Yes / No) See Table X
Prevalent AF patient	Binary variable (Yes / No) Equals to “Yes” if the patient is diagnosed AF during the historical period Patients belonging to the study population

9.4.3.4 *To describe the use of oral anticoagulants (OACs) in AF patients initiating treatment (AF patients exposed to OAC therapy)*

Table XVII. Derived variables for OAC treatment pattern

Variable	Definition

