Death	xx.x (xx.x)	xx.x (xx.x)	xx.x (xx.x)
Lost to follow-up	xx.x (xx.x)	xx.x (xx.x)	xx.x (xx.x)
End of study period	xx.x (xx.x)	xx.x (xx.x)	xx.x (xx.x)
Duration of the follow-up in years			
Mean (std)	xx.x (xx.x)	xx.x (xx.x)	xx.x (xx.x)
Median	xx.x	xx.x	xx.x
Q1 - Q3	xx.x - xx.x	xx.x - xx.x	xx.x - xx.x
Min - Max	xx.x - xx.x	xx.x - xx.x	xx.x - xx.x
Duration group of the follow-up in years: n (%)			
[0-1[xx.x (xx.x)	xx.x (xx.x)	xx.x (xx.x)
[1-2[xx.x (xx.x)	xx.x (xx.x)	xx.x (xx.x)
[2-3[xx.x (xx.x)	xx.x (xx.x)	xx.x (xx.x)
[3-4[xx.x (xx.x)	xx.x (xx.x)	xx.x (xx.x)
[4-5]*	xx.x (xx.x)	xx.x (xx.x)	xx.x (xx.x)

*This category will be display only for the sensitivity analysis (up to 2020)

2. Shell Tables and Figures of Results of the Planned Analysis for the Primary Objective

Table A2. Incidence rate for stroke, major bleeding and death in AF incidents patients between 2016 and 2019 in France – <POPULATION>

<POPULATION>	Stroke				Major bleeding				Death			
	n	N	Crude	Standardized **	n	N	Crude	Standardized %**	n	N	Crude	Standardized **
Overall	x	x	x,x [x,x;x,x]	NA	x	x	x,x [x,x;x,x]	NA	x	x	x,x [x,x;x,x]	NA
CI 95%				NA				NA				NA
Unexposed to OAC*	x	x	x,x [x,x;x,x]	x,x [x,x;x,x]	x	x	x,x [x,x;x,x]	x,x [x,x;x,x]	x	x	x,x [x,x;x,x]	x,x [x,x;x,x]
CI 95%												
Exposed to OAC	x	x	x,x [x,x;x,x]	NA	x	x	x,x [x,x;x,x]	NA	x	x	x,x [x,x;x,x]	NA
CI 95%				NA				NA				NA
VKAs	x	x	x,x [x,x;x,x]	NA	x	x	x,x [x,x;x,x]	NA	x	x	x,x [x,x;x,x]	NA
CI 95%				NA				NA				NA
DOACs	x	x	x,x [x,x;x,x]	NA	x	x	x,x [x,x;x,x]	NA	x	x	x,x [x,x;x,x]	NA
CI 95%				NA				NA				NA
Apixaban	x	x	x,x [x,x;x,x]	NA	x	x	x,x [x,x;x,x]	NA	x	x	x,x [x,x;x,x]	NA
CI 95%				NA				NA				NA
Dabigatran	x	x	x,x [x,x;x,x]	NA	x	x	x,x [x,x;x,x]	NA	x	x	x,x [x,x;x,x]	NA
CI 95%				NA				NA				NA
Rivaroxaban	x	x	x,x [x,x;x,x]	NA	x	x	x,x [x,x;x,x]	NA	x	x	x,x [x,x;x,x]	NA
CI 95%				NA				NA				NA

OAC: Oral anticoagulant; DOACs: Direct oral anticoagulants; VKAs: Antivitamins K; NA, not applicable.

n: number of events of interest; N: number of person-years of follow-up

*Unexposed and exposed to OAC correspond to the period of time where the patients are not exposed to OAC and exposed to OAC, respectively

%: Incidence of the event of interest; CI 95%: 95% confidence interval

**: Standardized on age group (<65 years old; 65-74 years old; 75-79 years old; ≥80 years old) using the exposed population as reference

<POPULATION>: Incidence rate of events will be stratified in the following sub-groups:

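### The adjusted Cox models enter age only as <80 / 80-90 / >90, so one coefficient covers ages 18 to 79 and some confounding by age stays in the hazard ratios

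*SAP*

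**What the plan says.** The Cox comparison of stroke, major bleeding and death (secondary objective 3) lists, in SAP 9.7.4.2, sex and "age (<80, 80-90, >90 years old") among the time-fixed confounders. Table XV defines the age confounder as "Categorical variable (<80 years old / 80–90 / >90 years old"). The shell note to Table A10 reads "Adjusted on the following covariates at index date: age (<80, 80-90, >90 years old), sex, having malnutrition" and continues with other conditions and treatments; the Table A11 note gives the same bands. SAP 9.7.6 plans no continuous, spline or finer-band age analysis.

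Elsewhere the SAP does divide the under-80s. The note to Table A2 says "Standardized on age group (<65 years old; 65-74 years old; 75-79 years old; ≥80 years old) using the exposed population as reference", and Table III uses the same four groups. Table XII lists age as "Continuous variable (year") but refers to Table III for the definition, and Table III defines only categories.

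Table XV also lists three scores that contain age: CHA2DS2-VASc as "Categorical variable (0, 1, 2, 3, 4, ≥ 5"), HAS-BLED and ACCI. Section 9.7.4.2 does not name them in its list but points to Table XV for the full set of confounders. The A10 and A11 notes leave them out.

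**The concern.** Age is a strong candidate confounder here: it plausibly drives all three outcomes and also the decision to anticoagulate. The documents show why the band below 80 matters. SAP 7.1 reports guidance to start an oral anticoagulant at a CHA2DS2-VASc score of 2 or more and to discuss it at 1. Table VI gives 1 point at 65-74 and 2 points from 75. The ages at which the treatment decision shifts, 65 and 75, therefore both lie inside the pooled band, where the age term cannot distinguish patients. If the exposure groups differ in age within a band, that difference is carried into the hazard ratio.

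**Working it through.** The plan states no figure for this point, so there is none to reproduce. The check asks how much age confounding three bands leave behind when the true exposure hazard ratio is 1.00.

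**Inputs.** From the documents: the three Cox bands (SAP 9.7.4.2), the four standardisation bands (Table A2 note), the score categories (Table XV), and two-thirds of AF patients aged 75 or over (SAP 7.1). Assumed, because the documents are silent: normally distributed ages, the mean and SD of age in each group, comorbidity, and a log-linear hazard rising 3%, 6% or 9% per year. Further runs used slopes up to 10%.

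**Method.** For rare events a Poisson model stands in for the Cox model. Expected events are proportional to person-time × h^age, with h = 1.03, 1.06 or 1.09 and no exposure effect. The exposure hazard ratio is then fitted under each age adjustment. Any departure from 1.00 is bias.

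**Equal spread (SD 11, overall mean 79.7, 66% aged 75 or over), range over the three slopes**

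| Mean shift between groups | Three bands | Three bands + scores |
|---|---|---|
| 1 year | 1.006-1.012 | 1.002-1.009 |
| 3 years | 1.017-1.035 | 1.006-1.027 |
| 5 years | 1.028-1.059 | 1.010-1.046 |

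Unadjusted, these scenarios give 1.027 to 1.438, so the three bands remove most of the confounding.

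**Unequal spread (60-66% aged 75 or over), hazard ratio B v A at slopes of 3% / 6% / 9%**

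| A: mean (SD) | B: mean (SD) | Three bands | Three bands + scores | Four bands |
|---|---|---|---|---|
| 79.7 (9) | 79.7 (14) | 0.974 / 0.988 / 1.027 | 1.010 / 1.022 / 1.055 | 1.046 / 1.127 / 1.243 |
| 78 (9) | 78 (14) | 0.968 / 0.979 / 1.017 | 1.008 / 1.018 / 1.051 | 1.042 / 1.125 / 1.248 |
| 80 (9) | 76 (14) | 0.948 / 0.948 / 0.979 | 1.002 / 1.000 / 1.022 | 1.023 / 1.076 / 1.154 |
| 82 (9) | 74 (13) | 0.931 / 0.915 / 0.929 | 0.994 / 0.974 / 0.977 | 0.994 / 1.000 / 1.015 |

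Continuous age returns 1.000 throughout. That is by construction, since the assumed age effect is log-linear; real data may need a curve.

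Three things follow:
- The three bands leave between 0.915 and 1.059, in either direction.
- The scores usually shrink the bias but do not remove it, and in a few rows they enlarge it (0.988 becomes 1.022; 1.027 becomes 1.055).
- The four bands do worse than the three in 8 of these 12 cells, because they pool everyone aged 80 and over.

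**Against precision.** 225,747 new users a year (SAP 9.5) × 4 years (2016-2019) = 902,988. If two compared groups had 5,000 events each (assumed), the 95% half-width on the log hazard ratio is 1.96 × √(1/5,000 + 1/5,000) = 0.039. With 10,000 each it is 0.028. A bias of a few percent is therefore as large as the random error.

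**The case against.** The strongest reply is that the model already carries age below 80 through the scores. Section 9.7.4.2 refers to Table XV for all confounders. CHA2DS2-VASc has age cut-points at 65 and 75, ACCI adds a point per decade from 50, and HAS-BLED splits at 65. The A10 note is also a poor guide to the covariate list, since it omits prescriber's specialty, which 9.7.4.2 names. Much of this stands: the scores probably do enter, so a reader should not infer that the model is blind to age below 80. They remain a partial remedy. Each mixes age with comorbidity, and the ACCI grouping in Table VI leaves totals of 5 to 9 with no category (its top group is labelled 5 or more but defined as 10 or more). A patient aged 70-79 with heart failure scores 3 + 2 = 5 and falls in that gap.

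A reader might also compute exp(slope × mean age difference below 80) and conclude that the bias is 15% to 65%: exp(0.07 × 2) = 1.15 and exp(0.10 × 5) = 1.65. That factor applies only inside the <80 band, whereas the model estimates one hazard ratio pooled over three bands. In the last row above, ages below 80 differ by 6.4 years. At 6% per year the formula gives 1.06^-6.4 = 0.69, while the pooled result is 0.915. In the first row the gap is 4.0 years; at 9% the formula gives 1.09^-4 = 0.71, while the pooled result is 1.027, on the other side of 1.

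Three further points are fair. The bands are the protocol's own stratification scheme (protocol 3.5.3), though nothing there requires them as the form of a confounder. The comparison is a secondary objective; the primary rates are descriptive and age-standardised separately. And the documents do not show that unexposed patients are the group most affected, because they give no ages by exposure.

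**Conclusion.** The point holds at a moderate size. Every statement of the Cox adjustment uses the three bands, nothing finer is planned, and the treatment-relevant ages 65 and 75 lie inside the widest band. The residual bias in the overall hazard ratio is roughly 1-8%, and about 0-5% if the Table XV scores are in the model. This rests on assumed mean age differences of 0 to 8 years, SDs of 9 to 14 and a hazard rising 3-10% per year. A mean difference nearer 10 years would push it past 10%, but nothing in the documents points to one. Direction cannot be stated. Bias of this size would not overturn a large effect, but it could move a narrow interval off the truth when the hazard ratio is close to 1.

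**What to change.** In all adjusted Cox models behind Tables A10 and A11, replace the banded term with age at index in years, entered as a restricted cubic spline. Five-year bands are an acceptable second choice. Keep <80 / 80-90 / >90 for stratified displays only, and do not substitute the four standardisation bands.

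Give continuous age its own definition in Table XII: year of index minus year of birth. SAP 9.3.1.2 lists "Date of birth (month and year") among the available data, so nothing new is needed. In the same edit, make 9.7.4.2, Table XV and the A10/A11 notes agree on whether the three scores are in the model, and close the ACCI gap at 5 to 9 points.

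The cost is one model term and a few lines of text, with negligible loss of precision at this cohort size. The small downside is that the coefficients of the age-containing scores change meaning once age is modelled finely beside them; this matters only if those coefficients are interpreted. Label: cheap improvement, close to free.
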